### **4. Phase 4 (Post treatment phase)**

This phase, which lasts 4 weeks, will begin after patients take their last dose of medication. All patients who complete at least 1 week of treatment will enter this phase. During this phase, study staff will contact patients periodically by phone or email to enquire how they are doing. Patients will fill out daily bowel diaries for 4 weeks and return them weekly for review. At the end of 4 weeks, they will be asked to complete post-treatment questionnaires to assess quality of life, anxiety and depression. They will also be asked to collect a single spot stool sample and mail them in. The questionnaires will be used to investigate if patients had worsening of symptoms after stopping therapy. The spot stool sample will be used to analyze the effect of treatment on the fecal microbiota. Participants will be asked record their dietary intake for 72 hours prior to collecting the stool sample and mail in the food record.

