### Abstract

**Background:** Available therapeutic options for idiopathic fecal incontinence (FI) are limited and unsatisfactory. There are no controlled studies documenting the efficacy of medications used to treat FI. We observed that oral clonidine significantly reduced diarrhea in patients with urge FI; while clonidine reduced the frequency of FI, effects were not statistically significant. Small uncontrolled studies suggest that the bile acid binding resin colesevelam also improves functional diarrhea. However, there are no controlled studies that have investigated the effect of colesevelam in FI. In this placebo controlled study, we plan to investigate the effects of combining colesevelam with clonidine on symptoms in women with FI. The primary aim of our study is to investigate the hypotheses that compared to placebo, colesevelam and clonidine will reduce the frequency of FI and rectal urgency. Additionally, we will also investigate the stool and mucosa associated microbiota in these patients at baseline and after treatment. The role of microbiota in pathogenesis of FI is unknown and we hope this study will offer us valuable insight into this question. Sixty women (18-80 y) with symptoms of urge or combined (i.e. urge and passive) FI will be recruited to this study and treated with a combination of colesevelam and clonidine or placebo for 4 weeks. The primary outcome will be the proportion of patients who achieve at least 50% reduction in the frequency of FI (number of FI episodes per Diem) at the end of 4 weeks of treatment.

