## **A. Specific Aims**

Fecal incontinence (FI) is a common symptom that can significantly impair quality of life. The current management of FI, particularly in patients with moderate to severe symptoms, is unsatisfactory. Our previous study showed that clonidine, a  $\alpha$ 2-agonist significantly decreased the proportion of loose stools in patients with urge or combined FI who also had diarrhea. While clonidine reduced the frequency of FI, effects were not statistically significant. A retrospective analysis of patients with bile acid malabsorption (BAM) observed that colesevelam, a bile acid binding resin improved subjective symptoms of FI in more than 70% patients. A prospective placebo controlled study on the impact of colesevelam in patients with FI is however lacking.

While BAM and alterations in fecal and colonic microbiota have been implicated to contribute to functional diarrhea and IBS respectively, the contribution of these disturbances to the pathogenesis or management of FI has not been evaluated. A better understanding of the same is necessary to guide the management of FI. Likewise, while IBS has been associated with gene polymorphisms, no studies have evaluated the association between gene polymorphisms and FI. Finally, the colonic mucosal microbiota are currently assessed by obtaining mucosal biopsies during a flexible sigmoidoscopy. It is conceivable that the mucosal microbiota can also be sampled with an rectal catheter. However, the characteristics of the colonic mucosal microbiota profile obtained with sigmoidoscopy and a catheter have not been compared.

The **central hypothesis** of this study is that a combination treatment with clonidine and colesevelam is better than placebo in reducing stool frequency and rectal urgency in FI. Additional hypotheses are that FI is associated with (i) BAM, (ii) alterations in the fecal and colonic mucosal microbiota, which are modified by treatment with colesevelam and clonidine and (iii) single nucleotide polymorphisms (SNPs) of selected genes.

In order to investigate these hypotheses we propose five aims as follows:

Aim 1: Compare the effects of combination treatment with colesevelam and clonidine vs. placebo on bowel symptoms in FI

Aim 2: Investigate the prevalence of BAM in patients with FI

Aim 3: Evaluate the fecal and colonic mucosal microbiota in patients with FI and the effects of treatment with colesevelam and clonidine

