**Exclusion criteria:**

- (i) Patients who completed less than 1 week of treatment with study drugs or placebo

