f) Fecal and colonic mucosal microbiome analysis: Microbial DNA will be extracted from stool and tissue samples using standardized methods [18]. Phylotype profiles of the microbiome from colesevelam and placebo treated FI populations will be generated using deep rDNA hypervariable tag sequencing of the hypervariable V3-V5 region of the SSU rRNA gene, which has been validated for use with human microbiomes and is one of the methods of choice for the HMP. With the longer reads from the MiSeq (250x250 paired end reads), our sequencing will include both the V3-V5 RGTs making for a more optimal phylogenetic analysis [19]. Phylotype profiles of the mucosa-associated microbiome will be generated using rDNA sequencing of the hypervariable V3-V5 region, which has been validated for standard use by the human microbiome project. The 500 base pair reads will ensure a better optimal phylogenetic identification. Barcoding samples prior to sequencing will yield approximately 20,000 reads/sample, ensuring detection of both dominant (core microbiome) and poorly represented taxa (variable microbiome). Identifying the existent taxa, diversity, and ecological relationships within each sample requires that we process large volumes of 16S DNA sequence data. In order to accomplish this task we will follow protocols that we have quantitatively shown to be optimal. Reads will be aligned using our own custom multiple alignment tool (TORNADO v2.0) that has been optimized the production of taxonomic calls and alignments for downstream analysis such as OTU clustering and phylogeny from paired end reads [20]. Sequences will be culled according to initial quality files using QIIME, pre clustered in order to reduce the number of unique reads due to sequencing errors using mother, and aligned using the new version of the TORNADO pipeline for paired end reads. TORNADO v2.0 will then be used to obtain the taxa calls that will be used in later correlation analysis. Second, quantitative PCR assays targeting functional genes mcrA and mrtA (methanogens) dsrA (sulfate-reducing bacteria) and hydA (hydrogen-producing bacteria) will be performed on both stool and mucosal samples following published protocols [21]. Similarly, different sulfate-reducing genera will be quantified with validated 16S primers. The abundance

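### Mucosa is sampled only at baseline, the one follow-up stool is collected after drug is stopped, and no test is named for bile acid malabsorption, so Aims 2 and 3 do not match the sampling schedule

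*Combined protocol and SAP*

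**What the plan says.** **Aims.** The Abstract promises that "we will also investigate the stool and mucosa associated microbiota in these patients at baseline and after treatment". Hypothesis (ii) in section A refers to "alterations in the fecal and colonic mucosal microbiota, which are modified by treatment with colesevelam and clonidine", and Aim 3 asks about treatment effects on both the fecal and the mucosal communities. Hypothesis (i) and Aim 2 concern an association of fecal incontinence with BAM and the prevalence of BAM.

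**Follow-up stool.** Section C.1, Phase 4, says: "This phase, which lasts 4 weeks, will begin after patients take their last dose of medication". On who contributes, it says: "All patients who complete at least 1 week of treatment will enter this phase". The Phase 4 exclusion criterion in section C.2.D is the mirror image: "Patients who completed less than 1 week of treatment with study drugs or placebo". After describing questionnaires due at the end of the four weeks, the Phase 4 text continues: "They will also be asked to collect a single spot stool sample and mail them in". The purpose given is: "The spot stool sample will be used to analyze the effect of treatment on the fecal microbiota". A 72-hour food record precedes the sample.

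**Mucosa.** Section C.3, items c and d, places the optional sigmoidoscopy in Phase 1, and the catheter just before manometry or at the initial visit.

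**BAM.** Section C.1, Phase 1, states that the Phase 1 tests other than the pregnancy test and EKG serve Aims 2 to 5.

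**The concern.** A treatment effect on a biological measure needs at least one measurement after randomisation, at a time that fits the effect claimed. For mucosa there is none. For stool there is one, but it is taken after treatment has ended, while its stated purpose is the effect of treatment without qualification. If the arms do not differ at that point, the trial cannot say whether treatment did nothing to the fecal microbiota or did something that reversed after stopping. If they do differ, the finding is about persistence and should be reported as such.

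For BAM the risk is different. A prevalence needs a case definition. If the assay and cut-off are chosen after the data are in, the estimate depends on that choice. If no assay is run, the aim has no answer.

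**Working it through.** No figure in the plan bears on this point. The only power statement (about 33 per group) concerns the frequency of incontinence and says nothing about Aims 2 or 3. The check is an inventory of what the text collects in each phase, set against what the aims need.

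| Sample | Phase 1 | Phase 2 | Phase 3 (on drug) | Phase 4 (off drug) |
|---|---|---|---|---|
| Stool | 1 | 0 | 0 | 1 |
| Rectal catheter | 1 (all) | 0 | 0 | 0 |
| Mucosal biopsy | optional | 0 | 0 | 0 |
| Named bile-acid measure | 0 | 0 | 0 | 0 |

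Sources: section C.1 (Phases 1 to 4) and section C.3, items c, d, f and h. The Phase 3 text lists diaries, contacts and end-of-treatment questionnaires, and no biological sample.

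**Mucosa.** There are 0 time points after baseline, so neither a change from baseline nor a post-treatment comparison of arms can be formed. Baseline description and Aim 4 (catheter against biopsy) need only Phase 1 samples and remain feasible.

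**Stool.** Phase 4 lasts 4 × 7 = 28 days. The collection sentence carries no date of its own. It follows directly on the end-of-phase questionnaires, so the natural reading is about 28 days after the last dose. If any Phase 4 day were allowed, the gap would be 0 to 28 days. On either reading the sample is taken after dosing has ended. Three features limit what it shows:

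- It can estimate a difference between arms that remains after stopping. It cannot estimate the difference while drug is being taken.
- Women treated for less than one week do not enter Phase 4 and give no follow-up stool. Their number is not given.
- Under section C.3, item g, the ban on antidiarrheal drugs ends with Phase 3, and recording of loperamide is required for the treatment phase. Antidiarrheal use before the Phase 4 stool is therefore not restricted. The diaries continue in Phase 4, but the text does not say that they record such use then.

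**BAM.** The Phase 1 tests left to serve Aims 2 to 5 are manometry, stool (assigned to microbiota), blood (assigned to genotyping), the catheter and optional sigmoidoscopy. None is described as measuring bile acids. The analysis plan and endpoint list in section C.4 give no BAM definition, cut-off or analysis.

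**The case against.** The strongest reply concerns the stool. No part of the protocol plans an on-treatment stool measure. The Abstract says after treatment, and the sample sits in a phase named post-treatment. A difference between randomised arms after stopping is itself an effect of treatment. The statement in section C.3, item f, that "Phylotype profiles of the microbiome from colesevelam and placebo treated FI populations will be generated" names the arms and does not imply sampling during dosing. This stands. A reader might infer that the fecal part of Aim 3 cannot be estimated at all, or that a planned on-drug measure was omitted. The documents support neither. What remains is a loosely stated target, an undated sample and an ambiguous null result.

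A second tempting inference is that no material is left for a bile-acid assay, because the blood total of 27.5 ml equals the 20 ml listed for DNA plus the 7.5 ml listed for RNA. That does not follow. Section C.3, item h, takes DNA from the buffy coat and stores the plasma frozen, and stool is also held. Section D mentions an immunochemical core laboratory, but names no bile-acid assay there. An assay may be possible. The gap is that none is specified.

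Third, Figure 1 is not shown and could contain an extra sample. That cannot be excluded, but the detailed phase text lists none.

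No counter-argument was found for the mucosal gap.

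**Conclusion.** The point holds, with three parts of unequal weight.

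- **Mucosa:** a plain mismatch between aims and procedures. With 0 post-baseline time points, the stated treatment effect cannot be estimated.
- **Stool:** a mismatch between timing and stated purpose. The comparison of arms is legitimate for persistence after stopping, most naturally at about 28 days, among women treated for at least one week. It does not speak to the effect during treatment, and a null result is ambiguous.
- **BAM:** mainly missing specification. The statement that the listed Phase 1 tests serve Aim 2 has no support in the described tests.

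This assumes that the text lists all collections (Figure 1 unseen) and that the stool is due at the end of Phase 4. A reader might take these gaps as weakening the efficacy result. They do not: Aim 1 and the primary endpoint use none of these samples. No bias or loss of precision can be quantified from the documents.

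**What to change.** 1. **Mucosa.** Restrict the mucosal statements in the Abstract, hypothesis (ii) and Aim 3 to baseline description. This costs wording only.

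2. **Stool.** Choose one of two routes.
   - Collect the same mailed stool and 72-hour food record in the last days of Phase 3. For women who stop early, including those under one week, collect at or soon after stopping. Record days since last dose, report them by arm, and compare arms as randomised. As the sample is mailed, no visit is added. The only extra samples come from women who stop before one week. The price is that off-drug persistence is no longer measured, some early stoppers' samples will be off drug, and the stool is taken while rescue loperamide is allowed. That use is at least recorded and is already a secondary endpoint.
   - Or keep the Phase 4 sample, fix its collection day, and state the stool part of Aim 3 as persistence after stopping. This costs wording only, but gives up the on-treatment question.

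3. **BAM.** Before analysis, name an assay, a case definition and a cut-off on samples already held (baseline stool or stored plasma), if they are suitable. Otherwise drop Aim 2 and hypothesis (i). The first choice costs the assay; the second costs the aim.

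The stool decision is needed while women are still being treated, because an on-drug sample cannot be recovered afterwards.

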## **2. Human subjects.**

Eligibility criteria for each phase of the study are tabulated below.

### **A. Phase 1**

Inclusion Criteria:

- i) Females aged 18-80 years with urge predominant or combined (i.e. urge plus passive) FI, as defined by a validated questionnaire, for ≥ 1 year duration will be eligible to participate.

Exclusion Criteria:

- (i) History of clinically serious cardiovascular or pulmonary disease or EKG showing 2nd degree atrioventricular block or higher.
- (ii) Current or past history of colon or rectal cancer, scleroderma, inflammatory bowel disease, ischemic colitis, small bowel obstruction, congenital anorectal abnormalities, ≥ Grade 2 rectal prolapse, history of rectal resection or pelvic irradiation

- (iii) Neurological disorders – Spinal cord injuries, dementia (Mini-Mental status score <21), multiple sclerosis, Parkinson's disease, peripheral neuropathy
- (iv) Conditions precluding safe use of clonidine, i.e., symptomatic hypotension, or systolic blood pressure of <100 mm Hg on initial visit in Phase 1 of study
- (v) Colon resection greater than limited resection (e.g. sigmoid colectomy for diverticulitis is eligible but right hemicolectomy is not)
- (vi) Patients who are currently on or anytime in the past have been on colesevelam for FI
- (vii) Malabsorptive bariatric procedures (i.e., Biliopancreatic diversion with or without duodenal switch and Jejunoileal bypass), gastric bypass surgery (i.e., Roux en Y gastric bypass) will be excluded. Those patients who have undergone restrictive procedures (e.g. vertical banded gastroplasty, laparoscopic adjustable gastric banding) however will be eligible to participate
- (viii) Currently pregnant or nursing women Prior history of intolerance to clonidine or colesevelam
- (ix) History of sphincteroplasty, sacral nerve stimulator, previous injection of Solesta for treatment of FI
- (x) Medications
  - .
  - Relative – opioid analgesics , other antihypertensive agents (i.e. if there is concern about synergistic effects and hypotension). Patients using drugs with anticholinergic effects at high doses (e.g. nortriptyline greater than 50 mg/day or amitriptyline greater than 25 mg/day) will be excluded at the discretion of the physician. Patients who use lower doses will be eligible to participate provided the dose will be stable during the study

## **B. Phase 2**

### Inclusion Criteria:

- i) Females aged 18-80 years with urge predominant or combined (i.e. urge plus passive) FI for  $\geq 1$  year, as defined by questionnaire

### Exclusion criteria:

- (i) Positive urine pregnancy screen

## **C. Phase 3**

### Inclusion criteria:

- (i) Completion of at least 5 out of 7 days of the diary in the preceding week and 10 out of 14 in the preceding 2 weeks
- (ii) At least 1 episode of FI per week averaged over 2 weeks
- (iii) Average Bristol stool score of 3 or higher
- (iv) Average stool frequency of  $\geq 1$ /day

### Exclusion criteria (if at least one is satisfied):

- (i) Missing data in bowel diaries, i.e. if patient did not record bowel symptoms data for more than 2 days in 1 week or 4 days over 2 weeks
- (ii) Greater than 6 liquid [Bristol 6 or 7] stools daily
- (iii) Average of less than 1 bowel movement daily
- (iv) Average Bristol stool score <3 as assessed from analysis of bowel diaries

## **D. Phase 4**

**Inclusion criteria:**

- (i) All patients who complete at least 1 week of treatment with study drugs or placebo

**Exclusion criteria:**

- (i) Patients who completed less than 1 week of treatment with study drugs or placebo

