### **3. Phase 3 (Treatment Phase)**

Patients who satisfy symptom criteria in Phase 2 will be randomized in a 1:1 ratio to receive either a combination of colesevelam (1.875 gm twice daily) and clonidine (0.1 mg oral twice daily) or an identical placebo for 4 weeks. The randomization, to be prepared by [name], will be balanced on age (<50 vs. ≥ 50 y) and BMI (<30 vs. ≥ 30 kg/m^2). Patients will fill *daily* bowel diaries for the entire duration of the treatment phase and mail them in every week. Patients will be contacted periodically (by phone or email) to assess compliance with medications, with filling bowel diaries and for any adverse events. At the end of the treatment phase, patients will be asked to fill questionnaires pertaining to their quality of life and satisfaction with treatment. During the treatment phase, patients will be allowed to use rescue medication in the form of loperamide to circumvent the potential for withdrawal from the study due to overwhelming symptoms. Patients are allowed to take loperamide (2mg/dose) up to 3 unit doses in a 24 hour period, 5 unit doses in a 48 hour period or 10 unit doses in any 7-day period. Patients will need to record their loperamide usage in the bowel diary.

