## **D. Human Subjects**

Only subjects who satisfy stringent inclusion and exclusion criteria and provide written informed consent will be included in the protocol. The consent form details issues related to privacy, withdrawal from studies, and use of blood for genetic analyses among other items. Additional details as follows:

1. **Anorectal assessments** are extremely safe; discomfort, if any during rectal distention is mild and tolerable and the risk of rectal perforation in an uninflamed rectum is negligible.
2. **Clonidine** is generally well tolerated at this dose. In a recent study, we observed that the most common side effect with clonidine was dry mouth (about 70% vs. 4.5% in placebo). Other adverse effects included drowsiness (23% vs 14% in placebo), light headedness (27% vs. 9% in placebo) and fatigue (36% vs. 23% in placebo) although they did not reach statistical significance.
3. **Colesevelam** is generally well tolerated at this dose. The most commonly reported side effects from Colesevelam are constipation, diarrhea, dyspepsia, hypoglycemia (mild and well tolerated), headache, abdominal cramps, nausea, and flatulence and back pain. Their frequency ranges from 8%-40% in different studies.

Patients will be appropriately screened and subjects with an increased risk of complications will be excluded from the study. All side effects will be recorded at the follow-up visit. Since the effects of clonidine and colesevelam in pregnant and nursing women are unknown, women who are pregnant or nursing will be excluded from the study. Women of child-bearing potential will be advised to employ contraceptive measures during the study and a pregnancy test will be checked before beginning clonidine or colesevelam.

Patients who cannot tolerate clonidine 0.1 mg bid will be switched to 0.1 mg once daily (qhs) Clonidine will be discontinued if:-

- (i) Subjects have syncope, or lethargy that interferes with safe performance of the volunteer's activities of daily living; or
- (ii) if the systolic blood pressure drops to < 90 mmHg for patients with a systolic BP between 90 and 130 mmHg, or if systolic BP falls to < 100 mmHg for subjects with a pre-treatment systolic BP > 130 mmHg; or
- (iii) if a subject becomes pregnant during the study.

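### Women who stop all study treatment in days 1 to 6 are barred from the only phase after the last dose, so no follow-up is scheduled for them and the post-treatment intent-to-treat comparison lacks their data

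*Combined protocol and SAP*

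**What the plan says.** Section C.1, Phase 4 (Post treatment phase), places this phase after treatment: "This phase, which lasts 4 weeks, will begin after patients take their last dose of medication". Entry depends on exposure: "All patients who complete at least 1 week of treatment will enter this phase". Section C.2.D repeats the condition as an inclusion criterion and then as an exclusion criterion: "Patients who completed less than 1 week of treatment with study drugs or placebo".

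During Phase 4, "study staff will contact patients periodically by phone or email to enquire how they are doing". Women also keep daily diaries, complete closing questionnaires and send in a stool sample. The stated purpose of the questionnaires concerns bowel symptoms: "The questionnaires will be used to investigate if patients had worsening of symptoms after stopping therapy". Adverse events are not named as a topic of the Phase 4 contacts.

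Adverse events are named in Section C.1, Phase 3: "Patients will be contacted periodically (by phone or email) to assess compliance with medications, with filling bowel diaries and for any adverse events". Women in that phase also keep daily "bowel diaries for the entire duration of the treatment phase and mail them in every week". No minimum exposure applies to either.

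Section D lists the events that end clonidine. One is "Subjects have syncope, or lethargy that interferes with safe performance of the volunteer's activities of daily living"; the others are falls in systolic blood pressure and pregnancy. For colesevelam, pregnancy is the only stated reason to stop. Section D also says that side effects are recorded at a follow-up visit, which is not defined or placed in any phase.

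Section C.4.ii (Data Analysis Plan) compares the arms over the treatment period and, separately, post-treatment. It calls for intent-to-treat analysis of everyone randomised, with imputation of missing values. Table 1 schedules the HAD in Phases 1 and 4 only.

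**The concern.** Entry to follow-up depends on something that happens after randomisation, namely how long a woman stays on treatment. Tolerability can affect that, and tolerability may differ by arm. Two things are at stake.

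The first is safety. The adverse event grades in Section D depend partly on outcome: whether the event resolved with treatment, or needed professional medical attention. If an event is still open when a woman stops on day 4, the plan states no scheduled point at which its outcome is learned. An event that begins after her last dose would be known only if she or her medical team reported it.

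The second is the analysis. The post-treatment comparison is meant to cover everyone randomised, yet the entry rule prevents collection of post-treatment data from some of them. The HAD score is a secondary endpoint in Section C.4.ii, and Section C.4.iii uses it as the trigger for offering psychiatric referral. An early stopper would have no HAD value after baseline.

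**Working it through.** The plan gives no figure for early stopping, so there is nothing to reproduce. The check sets the provisions side by side and then sizes the affected group under stated assumptions.

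**Follow-up stated for a woman who stops all treatment in days 1 to 6**

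| Provision | Section | Does it reach her after her last dose? |
|---|---|---|
| Phase 4 contacts, diaries, questionnaires | C.1 Phase 4; C.2.D | No, excluded by rule |
| Phase 3 contacts about adverse events | C.1 Phase 3 | Not stated whether they continue after early stopping |
| Phase 3 diaries | C.1 Phase 3 | Not stated |
| Follow-up visit for side effects | D | Visit undefined |
| Documentation of reported events; weekly review of rates | D, Data Safety and Monitoring Plan | Yes, but only if someone reports; no enquiry is scheduled |
| HAD after baseline | Table 1 | No, given only in Phase 4 |

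The supported statement is therefore that no scheduled post-dose contact is stated for her.

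**Size of the group**

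Inputs: 30 women per arm (60 in the Abstract, randomised 1:1) and an assumed share p stopping in week 1.

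Expected number per arm = 30p. Chance of at least one = 1 − (1 − p)^30.

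- p = 0.03: 30 × 0.03 = 0.9; 1 − 0.97^30 = 0.60
- p = 0.05: 30 × 0.05 = 1.5; 1 − 0.95^30 = 0.79
- p = 0.10: 30 × 0.10 = 3.0; 1 − 0.90^30 = 0.96

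The power statement implies 33 per arm. The expected numbers are then 1.65 at 5% and 3.3 at 10%, with chances of 0.82 and 0.97. These are counts of women who stop for any reason. They are not counts of missed events.

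**Possible effect on an event rate (illustration only)**

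Consider only events that begin after the last dose. Assume that 10% of women stop early, that 10% of those entering Phase 4 have such an event, and that none of the early stoppers' events is captured.

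- Early stoppers have the same 10% rate: true rate = 0.10 × 0.10 + 0.90 × 0.10 = 0.10; seen = 0.90 × 0.10 = 0.09 of all randomised.
- Early stoppers have a 50% rate: true rate = 0.10 × 0.50 + 0.90 × 0.10 = 0.14; seen = 0.09.

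The shortfall is 1 or 5 percentage points, depending wholly on inputs that the documents do not supply.

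**The case against.** A reader might infer that early stoppers get no contact at all and that the harm which made them stop goes unreported. The documents do not support that. Such harm arises on drug, in Phase 3, where staff ask about adverse events whatever the time on treatment. Section D documents qualifying events reported by the woman or her medical team, without limit of phase or exposure, and has rates reviewed weekly. Section C.4.iii adds monitoring by study personnel and the principal investigator. This part of the objection stands, and it confines the safety gap to what happens after the last dose.

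The route to exclusion is also narrower than it first appears. Syncope, lethargy and low blood pressure end clonidine, not colesevelam, and both drugs have dose-reduction steps for intolerance. A woman who stops clonidine on day 3 might continue colesevelam, and the plan does not say whether that counts as a week of treatment. Pregnancy is the one listed event that stops both drugs, and a test is required before dosing. This stands too: the number affected may be small.

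Phase 4 is not presented as safety follow-up. It looks for symptom worsening and microbiota change, and a minimum exposure is defensible for those aims. No Phase 4 safety summary is planned that the rule could distort. That explains the rule, but it does not supply follow-up elsewhere.

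Finally, imputation could fill the post-treatment gap. It could, but the values would then be missing because the plan declines to collect them, and a phone call or diary could often supply them.

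**Conclusion.** The point holds in limited form. The exclusion is an explicit rule, it selects on post-randomisation exposure, and it leaves women who stop all treatment in week 1 with no stated scheduled contact, diary or questionnaire after the last dose. It conflicts with the intent-to-treat statement for the post-treatment comparison and removes any HAD value after baseline for these women.

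It would be tempting to conclude that the combination will look safer than it is. The documents contain no discontinuation data, no rate by arm and no post-dose event rate, so neither under-reporting nor a difference between arms is shown. The estimate of roughly 1 to 3 women per arm rests on the assumed 3% to 10% early-stop rate. In a trial of about 60 women, that is enough to justify an inexpensive change to data collection, but it does not undermine the trial.

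**What to change.** 1. In Section C.1 Phase 4 and Section C.2.D, remove the 1-week condition for data collection. Offer every randomised woman who took at least one dose the existing Phase 4 phone or email contacts, diaries and questionnaires, counted from her last dose. It then no longer matters whether partial treatment amounts to a week.
2. State that adverse events are asked about at those contacts and that the outcome of any ongoing event is recorded up to the end of Phase 4.
3. In Section D, say when the follow-up visit takes place and that it includes early stoppers.
4. Summarise adverse events by arm in all women who took at least one dose.
5. Reconcile the Phase 4 entry rule with the intent-to-treat statement in Section C.4.ii, including how a randomised woman who never took a dose enters the post-treatment comparison.

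The cost is amendment wording and a few extra contacts, with no new staff or procedure. Some early stoppers will decline, and their data will still be missing. Nothing here changes dosing or the rules for stopping treatment.
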